In this study, with the assistance of endoscopic technology and intraoperative navigation technology, the removal and curettage of large odontogenic jaw cyst occurred in the mandible were performed to reduce the rate of postoperative nerve injury. A series of complications, such as residual lesion, pathological fracture, nerve injury and so on, were caused by the enlargement of incision due to limited visual field and the doubt in determining the boundary of cyst. In this study, endoscopic technique enabled the surgeon to obtain sufficient field of view in small incision, better understand the characteristics of the lesion, protect the inferior alveolar neurovascular bundle, prevent intraoperative pathological fracture and shorten the operation time. The intraoperative navigation technology allows doctors to accurately locate the anatomical positions of each bone in the maxillofacial region, and the navigation probe can accurately judge each orientation of the sac cavity. At the same time, the adapter is used to integrate the navigation and endoscopy, so that the endoscope can not only play the role of obtaining a clear vision but also play the function of real-time positioning. In this study, we compared the efficacy of traditional extraction and curettage with endoscopic navigation assistance in the treatment of giant mandibular bone cysts. In this study, the rate of inferior alveolar nerve injury 1 month after surgery was taken as the main outcome index, and the recurrence rate 1 year after surgery was taken as the secondary outcome index, to explore whether endoscopic combined with intraoperative navigation-assisted treatment of giant mandibular bone cyst could achieve lower postoperative nerve injury rate and postoperative recurrence rate.

II. Introduction

2.1 Research theoretical basis/background

Odontogenic jaw cyst is a unique disease affecting the mouth and mandible. Its occurrence is closely related to the development and formation of dental tissue and inflammation. The four most common odontogenic jaw cysts include periapical cyst, odontogenic cyst, residual cyst, and odontogenic keratosis cyst¹. Most cysts grow slowly and may have only mild or no symptoms. When cysts grow larger, they can damage the surrounding tissue, leading to maxillofacial swelling, infection, root resorption, nerve damage, pathological fracture, and even malocclusion². Smaller odontogenic jaw cysts can be removed directly by surgery, while the treatment of larger odontogenic jaw cysts remains controversial. Some scholars believe that fenestration decompression is an effective and conservative treatment³, but some scholars believe that although fenestration decompression is less traumatic, patients will be accompanied by discomfort during the long healing period, and direct surgery to remove the complete lesion is the best choice⁴.

In a previous retrospective study of 25 patients with large mandibular cysts who underwent traditional removal and curettage surgery, 8 patients developed symptoms of nerve damage after surgery, with a postoperative nerve damage rate of up to 32%.

It can be seen that how to effectively reduce the rate of nerve damage after surgery for giant mandibular bone cysts is still a difficult problem⁵. Related retrospective studies have shown that most jaw cysts occur in the anterior maxilla and molar areas of the mandible, and odontogenic jaw cysts are common in the mandible⁶. When the cyst lesion involves the mandibular branch, due to the high anatomical position, the surgeon cannot observe the full scope of the lesion under direct vision, and it is difficult to accurately locate the lesion boundary, which will increase the risk of residual lesion and postoperative recurrence, and bring difficulty and challenge to the operation. In addition, the inferior alveolar nerve passes through here, and if the location relationship between the nerve and the lesion is not clear, the risk of nerve injury will be greatly increased. When odontogenic maxillary cysts involving mandibular branches cannot be completely observed under direct vision, endoscopic techniques enable the surgeon to obtain sufficient visual field through small incisions, better understand the characteristics of the lesions, protect the inferior alveolar neurovascular bundles, prevent intraoperative pathological fractures and shorten the operation time⁸⁻¹⁰.

Although endoscope can help surgeons to clearly observe lesions and nerves, it cannot standard determine the anatomical position of each bone in maxillofacial region, the boundary of lesions and the anatomical relationship between lesions and nerves. Navigation technology provides a solution to this problem. In order to apply navigation technology in the operation, it is necessary to collect the data of the patient's lesion site before surgery, conduct 3D simulation and establish a model to clarify the anatomic relationship between the lesion and the surrounding tissue¹¹. During the operation, the reference frame should be fixed in the mandible, and the anatomical position of each bone in the maxillofacial region and the boundary of the lesion should be accurately located by the locator and probe, and the area reached by the probe or surgical instrument should be reflected in real time, so that the surgeon can accurately judge each orientation of the sac cavity¹²⁻¹⁴, and play a role in guiding the surgical route.

However, there are few studies on endoscopy combined with intraoperative navigation-assisted treatment of giant mandibular bone cysts. In this study, an innovative surgical scheme will be proposed to integrate endoscopy and navigation through the adapter, so that endoscopy can not only play the role of obtaining a clear vision but also play the function of real-time positioning, so as to achieve accurate surgery, aiming at reducing the postoperative nerve injury rate and postoperative recurrence rate of odontogenic jaw cyst, so as to obtain better clinical efficacy.

2.2 Risk/benefit evaluation

2.2.1 Known potential risks

(1) Accidental risk of general anesthesia: After patients receive general anesthesia, due to individual differences of patients, abnormal response to drugs may lead to severe suppression of respiratory and circulatory functions and malignant hyperthermia, etc., which can be life-threatening in severe cases. During anesthesia, various adverse reflexes may induce cardio-cerebrovascular accidents or cardiac and

respiratory arrest, leading to death. In the event of anaesthesia related adverse reactions, clinical treatment should be performed as a complication of normal surgery, while the patient's medical record is detailed and the possibility of continuing the clinical trial should be evaluated.

(2) Risk of tearing the inferior alveolar neurovascular bundle: When cystic lesions are severely attached to the nerve, there is a risk of nerve tearing when separating the mass, resulting in postoperative damage to the inferior alveolar nerve and numbness of the lower lip. When intraoperative nerve tears occur, intraoperative neuroanastomosis should be performed to preserve nerve function as much as possible.

(3) Risk of serious infection after surgery: When the scope of cystic lesions is too large, the risk of postoperative infection increases, and the wound in the operative area may not heal in one stage. In severe cases, it may spread to neighboring tissues, resulting in infection of the maxillofacial space. In the case of severe infection, anti-infection treatment should be actively applied. In the case of infection of maxillofacial space or severe edema of surrounding tissue, the existence of indications for incision and discharge of pus should be considered, and the vital signs of patients should be closely monitored.

(4) In this study, for patients with serious complications of anesthesia during perioperative period, severe postoperative infection or bleeding, respiratory distress caused by severe edema of surrounding tissues, and failure to reanastomosis of nerve tear, etc., the study intervention should be suspended and withdrawn from the study, clinical treatment of corresponding complications should be carried out, and patients should be actively treated. Specific measures should be the treatment plan mentioned in the above complications. The safety of the surgical method of the study protocol was discussed, and the follow-up was determined whether to adjust the study surgical protocol, and follow-up records of the original subjects were maintained during the suspension of the study. In the case of clear withdrawal, the investigator may continue to complete the follow-up without the study intervention.

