Two-point discrimination test: The distance between two points can be distinguished using a vernier caliper. The score ranges from 0 to 5, with 5 indicating no nerve damage.

Table 4: Two-point discrimination measurement rating table

Sign	Score
The distance between the two ends of the vernier caliper is > 15mm	0
The distance between the ends of the vernier caliper is 10-15mm	1
The distance between the ends of the vernier caliper is 9-10mm	2
The distance between the ends of the vernier caliper is 7-9mm	3
The distance between the ends of the vernier caliper is 5-7mm	4
The distance between both ends of the vernier caliper is less than 5mm	5

Figure 5 Vernier calipers measure the distance between two points¹⁵

Inferior alveolar nerve function was detected before and 1 month after surgery. Light touch detection 4 points, acupuncture detection 1 point, hot and cold stimulation 1 point, two-point discrimination detection 5 points showed no nerve damage. Any other score for any of the above is considered to be nerve damage.

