5.4.2 Data Analysis Set

Statistical analysis will be performed using SAS statistical analysis software (V.9.4, SAS Institute). If there is no special explanation, unilateral test will be used for the main index, and the control error α is 0.025; bilateral test will be used for the other indicators, and the error α is =0.05. If you need to calculate confidence intervals, calculate bilateral 95% confidence intervals unless otherwise specified.

- (1) full analysis set (FAS) : comprised of all subjects who underwent surgical treatment and were evaluated for efficacy. The data set is derived from all subjects by eliminating subjects in a minimal and reasonable way.
- (2) safety analysis set (SS) : A group of people who have received surgical treatment and have safety evaluation data. In the safety analysis, all patients will be analyzed according to the actual surgical group received.
- (3) per-protocol set (PPS) : all subjects who met the protocol and did not use concomitant drugs that affected the effectiveness evaluation, had good medication compliance (between 80% and 120%), and excluded subjects who had a major protocol violation and were judged to have a significant impact on the results. All trial protocol deviations that result in subjects being excluded from the conformance protocol set will be detailed in the Statistical Analysis Plan (SAP) and completed prior to data locking.

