7.2 Subject discontinuation/withdrawal from study

When subjects suspend or withdraw from the study due to dissatisfaction with the therapeutic effect of the study program or their own financial reasons, they should communicate with them to encourage them to actively treat the treatment and help them apply for public welfare funds to complete the treatment. In the perioperative period, if serious complications of anesthesia, serious postoperative infection or bleeding, respiratory distress caused by severe edema of surrounding tissues, nerve tears and other serious complications reached 30% of the number of subjects, the study should be suspended, and the safety of the surgical method of the study protocol should be discussed to determine whether to adjust the study surgical protocol, and follow-up should be conducted during the suspension of the study. Follow-up records of the original subjects were maintained. In the case of clear withdrawal, the investigator may continue to complete the follow-up without the study intervention.

7.3 Loss of access (measures to reduce loss of access and data loss due to loss of access)

After the enrollment of subjects, the researchers should keep the contact information of multiple subjects and the contact information of subjects' families. After the subjects are discharged from hospital, the researchers should actively contact the subjects by phone, timely understand the condition of the subjects, and arrange the subjects to be admitted to the hospital for the next stage of treatment in advance.

VIII. Adverse Events and unexpected events

An adverse event (AE) is an adverse medical event that occurs after a subject receives treatment, but is not necessarily causally related to the treatment. An adverse event may be any adverse and unexpected sign (including abnormal laboratory findings), symptom, or disease associated with the use of the treatment, regardless of whether it is related to the treatment. It includes, but is not limited to:

- (1) exacerbation of disease that existed before the study treatment was used;
- (2) Increased frequency or severity of paroxysmal events that existed before the study treatment was used;
- (3) abnormal changes detected or diagnosed after the study of treatment use, although such abnormal changes may have existed before treatment;
- (4) Exacerbation of disease or symptoms that were already persistent before the study began.

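### Patients with an irreparable nerve tear appear to be withdrawn with optional follow-up, so near-certain primary events can be dropped from the 1-month injury rate or imputed as uninjured

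*Protocol*

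**What the plan says.** The opening summary of the protocol states that "the rate of inferior alveolar nerve injury 1 month after surgery was taken as the main outcome index". Section 5.2.1 scores four sensory tests before surgery and at 1 month and defines the event by those scores alone: "Any other score for any of the above is considered to be nerve damage". The schedule in 5.2.3 has nerve testing only at V2 (preoperative) and V5 (1 month). Inclusion criterion (7) in 4.1 requires no inferior alveolar nerve injury before the operation.

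Section 2.2.1(2) describes an intraoperative tear as "resulting in postoperative damage to the inferior alveolar nerve and numbness of the lower lip". Item (4) of the same section lists, among its serious complications, "failure to reanastomosis of nerve tear, etc., the study intervention should be suspended and withdrawn from the study". It then adds the sentence repeated in 7.2: "In the case of clear withdrawal, the investigator may continue to complete the follow-up without the study intervention".

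Sections 7.1 and 7.2 name nearly the same complications, including nerve tears, but only as a trigger for suspending the whole study once they reach 30% of participants.

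Section 5.4.2 defines the full analysis set (FAS) as "comprised of all subjects who underwent surgical treatment and were evaluated for efficacy". The end of 5.4.3 fills missing primary data by LOCF.

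**The concern.** A torn nerve that could not be rejoined is, by the protocol's own account, very nearly the outcome that the trial counts. Making it a ground for withdrawal takes the patient out because of the outcome, before the outcome is scored. Nothing in 3.2.1 or 5.2.1 lets the surgical finding itself count as an injury, and nothing requires V5 after withdrawal.

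At stake is the trial's only confirmatory claim, a single-arm rate compared with a historical 32%. There is no concurrent arm in which the same loss could occur and partly cancel. Every event lost this way moves the estimate towards success.

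**Working it through.** **1. What happens to such a patient if V5 is not done**

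- Exclusion: the FAS wording requires an efficacy evaluation. With no V5 score the patient can be left out, which removes one event from the numerator and one subject from the denominator.
- LOCF: the only earlier nerve score is the preoperative one, which criterion (7) requires to show no injury. The patient stays in the denominator and is recorded as uninjured.

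The text does not say which route applies. Both lower the rate, LOCF more than exclusion.

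**2. The plan's own sample size**

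Inputs: p0 = 0.32 (8/25, section 2.1), p1 = 0.20 (section 5.1), one-sided α = 0.025 and power 80% (section 5.4.1).

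n = [(1.960·√(0.32·0.68) + 0.8416·√(0.20·0.80)) / 0.12]² = [(0.9143 + 0.3367)/0.12]² = 108.7, so 109. With 10% loss, 109/0.90 = 121.1, so 122. Both stated figures reproduce.

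**3. Success criterion used here**

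Assumption: success means the upper limit of the two-sided 95% Clopper-Pearson interval (the one-sided 97.5% limit) is below 32%. Section 5.4.3 names the lower limit, which is a separate matter. The upper limit for x injuries in n is the 0.975 quantile of Beta(x+1, n−x).

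- 25/109: 31.97%, passes.
- 26/109: 32.97%, fails.

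The cut-off is therefore 25 or fewer of 109, with exact one-sided error P(X ≤ 25 | 109, 0.32) = 0.0246.

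**4. Three lost patients**

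Suppose 27 of 109 operated patients are truly injured, three of them with irreparable tears and no V5.

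| Handling | Injuries/n | Rate | Upper limit | Result |
|---|---|---|---|---|
| All counted | 27/109 | 24.8% | 34.0% | fails |
| Three excluded | 24/106 | 22.6% | 31.8% | passes |
| Three filled by LOCF | 24/109 | 22.0% | 31.0% | passes |

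The routes do not always agree. With 28 true injuries and three lost, exclusion gives 25/106 (32.8%, fails), while LOCF gives 25/109 (31.97%, passes by 0.03 percentage points).

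**5. Chance of false success when the true rate is 32%**

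Let f be the proportion of all operated patients with an irreparable tear and no V5. The documents give no value, so a range is shown.

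- LOCF: P(X ≤ 25 | 109, 0.32 − f).
- Exclusion: the number lost is W ~ Bin(109, f). The rest have rate (0.32 − f)/(1 − f), and the cut-off is recomputed for each 109 − W and averaged over W.

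| f | Excluded | LOCF |
|---|---|---|
| 0 | 2.5% | 2.5% |
| 0.5% | 2.6% | 3.2% |
| 1% | 2.9% | 4.0% |
| 2% | 3.9% | 6.4% |
| 3% | 5.3% | 9.7% |
| 5% | 9.7% | 20.0% |

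**The case against.** **Loss is permitted, not prescribed.** Section 6.3 asks subjects to return at 1 month for the nerve test and writes no exception for complications. Section VIII lists the nerve tear as a possible adverse event and calls for its outcome to be recorded and followed. The FAS text says eliminations should be minimal and reasonable. Section 2.2.1(4) also says that "follow-up records of the original subjects were maintained during the suspension of the study". This stands to the extent that a conscientious team could obtain V5 for every such patient. It does not close the gap. The follow-up sentence concerns a suspension of the study, an adverse event record is not a primary endpoint score, and no passage requires V5 after withdrawal or assigns an outcome without it.

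**Patient-level withdrawal is not certain.** The grammatical subject in 2.2.1(4) is the study intervention, and 7.1 and 7.2 tie similar complications only to a study-level suspension. The opening reference to patients with the complication and the later mention of clear withdrawal make the patient-level reading the most natural one, but these sections must be reconciled.

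**The frequency is unknown.** The 8/25 history gives nerve damage, not tears. At a 32% injury rate, f = 5% would make about 16% of all injuries irreparable tears (5/32). At 0.5%, exclusion barely moves the error. This stands, and it limits what can be said about size, not direction.

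**The analysis plan could settle it.** Such a plan may exist, but the withdrawal wording, the optional follow-up, the FAS and LOCF are all fixed in this protocol, and together they create the problem.

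**Conclusion.** The point holds. If a patient with an irreparable tear is withdrawn and not tested at V5, the plan either drops that patient or records an uninjured nerve, and both errors favour the technique. Three such patients among 109 can turn a failed result into a success.

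The size rests on three assumptions: success judged on the upper limit against 32%, every such patient missing V5, and a tear frequency that the documents do not give. Over 0.5% to 5% of patients, false success runs from 2.6% to 9.7% under exclusion and from 3.2% to 20.0% under LOCF, against a nominal 2.5%.

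A reader might infer that the protocol orders these patients to be discarded, or that the trial's error rate will be of the order of 10% to 20%. The documents support neither. Follow-up is allowed, the withdrawal text is loosely worded, and the larger figures need both a high tear frequency and complete loss of V5.

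**What to change.** Leave the clinical handling of the complication as it is and change the outcome and analysis rules.

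1. Sections 3.2.1 and 5.2.1: an intraoperative inferior alveolar nerve tear with failed anastomosis counts as a primary-endpoint injury, whether or not V5 is done.
2. Section 5.4.2: define the FAS for the primary endpoint as all operated subjects.
3. Section 5.4.3: replace LOCF for the primary endpoint. This must accompany item 2, because widening the FAS while LOCF stays would record the other withdrawn patients without V5 as uninjured. One option is to count a missing V5 as injury, with a complete-case sensitivity analysis.
4. Sections 2.2.1(4) and 7.2: state that withdrawn subjects will be asked to complete the V5 nerve test unless they withdraw consent.
5. Reconcile 2.2.1(4) with 7.1 and 7.2 on whether the patient, the intervention or the study is stopped.

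The cost is a short amendment and no extra visits. Item 1 may make the reported rate slightly less favourable. The option in item 3 costs more if losses are large. If the whole planned 10% loss were missing V5 results, a true 20% would appear as 0.90 × 20% + 10% = 28%, or about 34 of 122. The cut-off there is 28 (28/122 has upper limit 31.4%, 29/122 has 32.3%). That option therefore needs V5 losses kept well below 10%. Otherwise another rule that does not rely on the preoperative score should be primary, with missing counted as injury as the sensitivity analysis. Items 1 and 4 are needed in either case.

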2.2.2 Known potential benefits

The potential benefits of this study include safer and more effective surgery, complete curettage of cystic lesions and protection of the associated normal anatomical structure. It can better protect lower alveolar neurovascular bundle, prevent intraoperative pathological fracture and shorten operative time. The operation is minimally invasive and the patients recover faster after operation. Subjects entering this clinical study can reduce the surgical cost of endoscopic technology, gain more attention from researchers and timely treatment of disease changes, which is conducive to the treatment of subjects' diseases.

2.2.3 Potential risk and benefit evaluation

In this study, endoscopy combined with intraoperative navigation assisted treatment of giant mandibular bone cysts was adopted. Endoscopy technology provided surgeons with a clearer and more complete surgical field of view, while

navigation technology could reflect the relationship and position between surgical instruments and the patient's anatomical structure in real time, allowing surgeons to obtain clear and objective anatomical recognition during surgery. Preoperative computer simulation combined with intraoperative navigation has been proven to be an effective way to improve surgical outcomes. In this study, endoscopic techniques combined with intraoperative navigation techniques were used to treat large odontogenic maxillary cysts involving mandibular branches, which were not only safe and effective, but also able to completely curettage cystic lesions during the operation and protect the associated normal anatomical structures. It can better protect the lower alveolar neurovascular bundle, prevent intraoperative pathological fracture and shorten the operation time. This procedure is minimally invasive and patients recover faster after surgery. As a result, patients have a lower risk of developing nerve tears during surgery. In addition, each patient will undergo various basic examinations before surgery to strictly evaluate whether they can tolerate general anesthesia surgery and reduce the risk of anesthesia accidents. In future studies, researchers will pay more attention to the subjects' systemic conditions and tumor treatment, and the subjects will also obtain certain clinical benefits in this study.

III. Purpose and endpoint of the study

